9 RATIONALE AND BACKGROUND

Respiratory syncytial virus (RSV) is a common pathogen causing respiratory tract infections [3], and its burden is increasingly recognised among older adults. In high-income countries, RSV-related annual hospitalisations were estimated to be 787,000 in 2021 [4], with an annual hospitalisation rate of 145 per 100,000 for RSV-associated acute respiratory infections in adults \geq 60 years of age [5]. In older adults, RSV case fatality proportion was estimated to be 8% [6], with both hospitalisation and mortality rates found to be comparable to influenza [7]. Adults with underlying medical conditions [8, 9] and frailty [10, 11] are at higher risk for hospitalisation and death, potentially due to exacerbation of existing chronic conditions, such as chronic obstructive pulmonary disease and congestive heart failure.

RSV has two main subtypes: A and B, with either of them predominating in a given season, although they may circulate simultaneously in the population [12]. In temperate climates, RSV typically follows a distinct seasonal pattern, with a peak between December and February. Reverse transcriptasepolymerase chain reaction (RT-PCR) and (PCR-based) point-of-care (POC) tests are the gold-standard for the diagnosis of RSV infections. Rapid antigen detection tests (RADT) are also used for the RSV diagnosis, as they require less time and resources, but have a lower sensitivity [13]. Clinical severity is strongly associated with viral load, which declines seven days after inoculation [14].

The development of safe and efficacious vaccination products is essential in addressing the public health impact of RSV-associated illness. Two protein-based vaccines have been approved for use in adults 60 years and older. As of 20 November 2023, the following RSV vaccines are authorised for use in the EU: Arexvy[®] (GSK) and Abrysvo[®] (Pfizer).

Although the efficacy of RSV vaccines has been investigated thoroughly during clinical trials, continuous evaluation of product-specific vaccine effectiveness (VE) under real-world conditions once used as part of the national immunisation programmes (NIPs) remains crucial. Real-world studies allow for the evaluation of more rare outcomes such as hospitalisation. Additionally, duration of vaccine-induced protection, differential VE based on RSV subtypes, and VE in risk groups such as immunocompromised or patients with chronic conditions can be assessed.

Id.DRIVE, a not-for-profit public-private partnership (PPP) launched in January 2024, is leveraging COVIDRIVE, a PPP that addressed the joint need to monitor coronavirus disease 2019 (COVID-19) vaccination programmes for public health institutes and assess brand-specific COVID-19 vaccine effectiveness for vaccine companies as part of their regulatory obligations. Id.DRIVE will facilitate the conduct of studies on infectious diseases' burden, -vaccines, -preventive measures, and -therapeutics (e.g. antivirals, monoclonal antibodies) in the European region. Current id.DRIVE members are FISABIO (Fundación para el Fomento de la Investigación Sanitaria y Biomédica de la Comunitat Valenciana, Spain), P95 epidemiology & Pharmacovigilance (Belgium), AstraZeneca (UK), GSK (GlaxoSmithKline, Belgium), Janssen (Belgium), Novavax (US), Pfizer (US), and Valneva (France). The Pharmaceutical Company Partner will use this partnership to conduct its future RSV VE studies as part of its European regulatory obligations.

This Study Requestor-specific protocol describes a non-interventional study to estimate the effectiveness of RSV vaccines against RSV-related hospitalisations through the id.DRIVE partnership.

Confidential

Version 2.0

This study is a multi-centre, hospital-based, case-control study with test-negative controls (testnegative case-control [TNCC] design). The hospital-based TNCC design is efficient for studying rare outcomes, allows potentially for patient-reported or healthcare provider-reported data collection, and can minimise disease misclassification and confounding by healthcare-seeking behaviour. Data will be collected through a wide network of hospitals located in several European countries.

The outline of this Study Requestor-specific protocol was inspired by the Preparing for RSV Immunisation and Surveillance in Europe (PROMISE) project (https://imi-promise.eu) and the COVIDRIVE project (https://iddrive.eu/).

10 RESEARCH QUESTION AND OBJECTIVES

10.1 Research question

The study aims to continuously monitor VE of an RSV vaccine of interest against RSV-related modified SARI hospitalisations at the vaccine brand/product-specific level using a network of hospitals across Europe.

10.2 Research objectives

10.2.1 Primary objective

Objective 1: to estimate brand-specific RSV VE against hospitalisation due to laboratoryconfirmed RSV infection in severe acute respiratory infection (modified SARI) older adult patients.

10.2.2 Secondary objectives

- Objective 2: as objective 1, but stratified by:
 - RSV subtype A and B infection (objective 2.1)
 population of special interest (e.g., age groups, gender)⁸ (objective 2.2)
 time since vaccination (objective 2.3)
 calendar time (objective 2.4)
 - modified severity level⁹
 (objective 2.5)

⁹ Severity levels are defined by hospital outcome (intensive care unit [ICU] admission; in-hospital death) and/or respiratory support. As an additional indicator of severity at hospitalisation and throughout hospitalisation, progression risk is defined as proportion of in-hospital deaths and proportion of [ICU] admissions among all hospitalised SARI patients.

⁸ For example, specific age groups, specific immunocompromised or chronic conditions

11 RESEARCH METHODS

11.1 Study design

This study is a multi-country¹⁰, multi-centre, hospital-based case-control study with TNCC design.

A combination of primary and secondary data collection will be used to obtain the relevant data. The Schedule of Activities (Figure 1) shows the primary data collected from subjects during the study period.

[figure not shown]

Figure 1. Schedule of activities for the primary data collection during the study period.

11.2 Study Contributors

In this study, the term 'Study Contributor' is used in lieu of 'study site'.

The participating Study Contributors are either individual hospitals or hospital networks. The data collection will be a prospective data collection from primary data sources (e.g., specific laboratory results) and secondary data sources (e.g., existing hospital databases, vaccine registries and linked data). Retrospective data collection will be considered to allow capture of whole epidemiological year data in Study Contributors with late set-up.

¹⁰ The list of countries will be extended as the id.DRIVE network grows.

11.3 Study population

11.3.1 Patient identification

Systematic screening of individuals presenting with respiratory symptoms at participating hospitals during the study period is organised. The study population consists of hospitalised¹¹ modified SARI patients. Those who fulfil all the inclusion criteria but not the exclusion criterion will be proposed to be part of the study. A modified SARI patient is a person hospitalised with a suspicion of a respiratory infection with at least one of the following symptoms:

- cough
- shortness of breath
- fever (≥38 C^o)

with symptom onset within the last 10 days prior to hospital admission. This SARI definition is modified from the latest European Centre for Disease Prevention and Control (ECDC) case definition [15] Sensitivity analysis will be done applying the WHO-RSV case definition¹² and id.DRIVE case definition¹³.

Participants may be co-enrolled in interventional trials. The name of the trial will be collected, to allow for exclusion from specific analysis, where required, and will be prespecified in the SAP.

11.3.2 Inclusion criteria

Individuals (patients) must fulfil all of the following inclusion criteria to be included in the study as study participants:

- The patient is ≥ 60 years old at the time of admission to the hospital.
- The patient is eligible to receive vaccination against RSV (depending on the vaccination programme in the patient's country of residence).
- Informed consent is obtained from the patient or from the patient's legally acceptable representative(s) (LAR(s)) prior to enrolment.

¹³ An id.DRIVE definition of SARI (defined as requiring hospitalisation with a suspicion of a respiratory infection with symptom onset within the last 14 days prior to hospital admission, having at least one of the following symptoms: cough, shortness of breath, fever (\geq 38 C°) or sudden onset of anosmia, ageusia or dysgeusia) will be used in sensitivity analyses. This SARI definition is modified from the latest ECDC case definition (specifying "suspicion of respiratory infection"). [EUROPEAN CENTRE FOR DISEASE PREVENTION AND CONTROL (2023). Core protocol for ECDC studies of COVID-19 vaccine effectiveness against hospitalisation with Severe Acute Respiratory Infection, laboratory-confirmed with SARS-CoV-2 or with seasonal influenza - Version 2.0. Available from: https://www.ecdc.europa.eu/en/publications-data/core-protocol-ecdcstudies-covid-19-vaccine-effectiveness-against-0 [Accessed: 17-08-2023]].

¹¹ The patient is hospitalised for minimum one whole night ("one overnight stay").

¹² A World Health Organisation (WHO)-expanded definition of RSV-SARI (severe disease – defined as requiring hospitalisation AND acute – defined as onset within the last 10 days AND respiratory infection – defined as having at least one of the following: shortness of breath or cough) will be used in sensitivity analyses. [Source: https://www.who.int/teams/global-influenza-programme/global-respiratory-syncytial-virus-surveillance/case-definitions]

11.3.3 Exclusion criteria

Individuals (patients) must not fulfil any of the following exclusion criteria to be included in the study as study participants:

• The patient is unable or unwilling to provide the protocol required respiratory specimen(s) for any reason.

11.4 Study period

The study provides continuous (i.e., year-round) RSV surveillance, with a study period lasting minimum one epidemiological year with a possible extension.

11.5 Study outcomes

11.5.1 Primary outcome: laboratory-confirmed RSV

The outcome of interest for the primary analysis will be RSV detection in patients hospitalised with symptoms consistent with the modified ECDC SARI definition.

To the extent possible, clinical specimens will be collected from the patients eligible for the study as part of routine clinical sampling for diagnostic work-up. However, depending on local practice, additional sampling for the purpose of the study may be required. Respiratory sampling should preferably be done in both the nasopharynx and oropharynx, using a stiff oropharynx swab or a flexible nasopharynx swab. Additional respiratory specimens are accepted (e.g., saliva/saline mouth wash, sputum, bronchoalveolar lavage, or aspirates), when collected as part of patient diagnostic work-up.

RSV infection must be laboratory-confirmed by RT-PCR or another RNA amplification system with at least the same sensitivity as RT-PCR (e.g., transcription-mediated amplification [TMA]). RT-PCR assays must be used for the detection of at least RSV, SARS-CoV-2, and influenza.

Only Study Contributors where laboratory confirmation is performed by RT-PCR or another RNA amplification system with similar sensitivity (e.g., transcription-mediated amplification [TMA]) are eligible to participate in the study.

11.5.2 Secondary outcomes

The secondary outcomes in patients hospitalised with modified SARI symptoms include:

- detection of RSV subtypes A and B
- modified SARI severity level of study participants (both cases and controls), including respiratory support severity level

11.5.2.1 RSV subtypes

Information on the RSV subtypes (A and B) will be collected to the extent possible, preferably on all confirmed RSV cases when sample quality allows.

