11.12.4 Statistical analyses

VE is defined as $(1 - OR) \times 100\%$, where *OR* denotes the (exposure) odds ratio, comparing the confounder-adjusted odds of vaccination among RSV-positive study participants to the odds of vaccination among RSV-negative study participants.

VE estimates will be adjusted for calendar time at minimum, and additionally the following confounders – age, sex, and comorbidities (e.g. number of chronic conditions). Adjustments are usually achieved through inclusion of the relevant terms in the logistic regression models, with (penalised) spline terms for calendar time and age. However, other methods may be considered as well.

Clusters will be defined at the hospital network (Study Contributor) level. If some networks have hospitals that are very different (e.g. geographically separated), then clustering could be defined at the hospital level for these networks. However, similarities between these hospitals may remain due to being part of the same hospital network, in which cases these would not be treated as being independent of each other.

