11.12.4.1 Missing values

Data on exposure and especially the potential confounders may be missing for a proportion of the study participants. These data are often collected from existing medical records, vaccine registries, etc. which existed before the modified SARI episode, and it seems reasonable to assume that whether the data is missing is independent of the RSV status during the modified SARI episode. Assuming that the described missing data mechanism holds, performing a complete case analysis (CCA) will not lead to biased results. The primary analysis will therefore be a CCA, dropping records with missing information for the outcome, exposure of interest or the covariates. In case >10% of the cases and controls have missing covariate information, CCA is likely to be inefficient and alternatives such as multiple imputation and augmented CCA will be explored. A sensitivity analysis will be carried out comparing results from CCA (where records with missing data are dropped) and full set analysis (with imputed data).

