- In Germany there is no vaccine registry available, and paper vaccination cards are used for documentation. In some cases, the vaccination card may not be available as a physical document at the time of hospital admission, thus, provision of the vaccination data card may be foreseen by relatives, which can be challenging. In addition, there is a chance of incomplete data because of unreadable handwriting on vaccination cards. Therefore, misclassification of vaccination status may be greater for data collected in German sites.
- The PROMISE generic RSV VE protocol recommends the exclusion of persons with a contraindication to the RSV vaccine being studied, in order to only capture the eligible population. Such patients are not excluded from the present study, as vaccine contraindications cannot be collected. However, numbers are expected to be small.
- Despite RT-PCR's high specificity and sensitivity, diagnostic inaccuracies pose potential bias, influenced by factors like sampling technique, specimen type, number of specimens [17, 18], and timing. In RSV RT-PCR, declining sensitivity over time may yield more false negatives among vaccinated, overestimating VE. Sensitivity analyses, such as varying time between symptom onset and sampling, as well as addition of pre-admission rapid antigen testing, will

explore potential misclassification bias. Study staff follow guidance for proper specimen collection, ensuring a robust testing procedure.

- Unaccounted potential confounders in this study, such as ethnicity and socio-economic status, could lead to overestimated VE when certain groups are less likely to be vaccinated. TNCC studies, limited to those accessing healthcare or hospitalised, may not generalise to disadvantaged groups with poor access or nursing home residents, affecting result applicability.
- This study does not measure frailty, an important potential effect modifier of VE. Frailty has been shown to affect immune responses in older adults to vaccines for infections such as influenza, shingles and pneumococcus [19]. Frailty, impacting immune responses in older adults, lacks a consensus definition and measurement method. Given the study's focus on the general population and frailty's complexity, we collect information on related variables like age, body mass index (BMI), long-term care residence, and chronic conditions instead of directly measuring frailty.

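### The complete-case justification in 11.12.4.1 does not reach missing RSV subtype, so subtype-specific VE (objective 2.1) may be biased if typing differs by vaccination status

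*Protocol*

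**What the plan says.** Section 11.5.2 lists "detection of RSV subtypes A and B" as a secondary outcome. Section 11.5.2.1, like the Abstract, asks for subtype as far as possible, "preferably on all confirmed RSV cases when sample quality allows". Section 10.2.2 defines the secondary objectives by reference to the primary one: "Objective 2: as objective 1, but stratified by", with subtype A and B as objective 2.1. Section 11.12.4 bases VE on an exposure odds ratio, "comparing the confounder-adjusted odds of vaccination among RSV-positive study participants to the odds of vaccination among RSV-negative study participants".

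On missing data, section 11.12.4.1 states: "The primary analysis will therefore be a CCA, dropping records with missing information for the outcome, exposure of interest or the covariates". The reason given is that exposure and confounder data come from records that existed before the episode, so that "it seems reasonable to assume that whether the data is missing is independent of the RSV status during the modified SARI episode". Alternatives such as multiple imputation are to be explored when more than 10% of cases and controls lack covariate information. The section also promises a sensitivity analysis that compares the complete-case result with an analysis of imputed data. It does not say which variables are imputed.

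Section 13 says of RSV RT-PCR that "declining sensitivity over time may yield more false negatives among vaccinated, overestimating VE".

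**The concern.** For objective 2.1 the outcome is the subtype. If the complete-case rule carries over, an RSV-positive patient without a subtype is a record with a missing outcome and is dropped. Controls need no subtype, so all of them stay.

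The argument that this is harmless has two parts, and neither fits subtype. The data did not exist before the episode, and missingness is not independent of RSV status, because only RSV-positives can lack a subtype. The 10% trigger names covariates only. Neither the sensitivity analyses listed in 11.12.4.2 nor the limitations in section 13 mention untyped cases.

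At stake is the validity of VE against A and against B. If typing differs by vaccination status, the vaccination odds among typed cases shift against an unchanged control group, and both subtype estimates move the same way. Both could then lie on the same side of the any-RSV VE, which correct estimates cannot do.

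**Working it through.** The protocol gives no typing rate, subtype VE or subtype sample size, so there is no figure of its own to reproduce. All typing rates, coverages and VE values below are assumptions.

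**1. Bias formula.** Let s_v and s_u be the probabilities that a vaccinated and an unvaccinated RSV case is typed. Dropping untyped cases multiplies the vaccinated case count by s_v and the unvaccinated case count by s_u, and leaves controls alone. Hence

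OR_obs = OR_true × (s_v / s_u), and VE_obs = 1 − (1 − VE) × (s_v / s_u).

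**2. Numbers for a true VE of 60% (OR 0.40).**

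| s_v / s_u | OR_obs | VE_obs |
|---|---|---|
| 0.60 | 0.40 × 0.60 = 0.24 | 76% |
| 0.75 (e.g. 60% v 80% typed) | 0.40 × 0.75 = 0.30 | 70% |
| 0.90 | 0.40 × 0.90 = 0.36 | 64% |
| 1.00 | 0.40 | 60% (no bias) |
| 1.125 (e.g. 90% v 80% typed) | 0.40 × 1.125 = 0.45 | 55% |

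Incomplete typing alone does no harm: with 80% typed in both groups, 20% of cases are lost and VE is unchanged. The bias did not vary with coverage between 5% and 40%.

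**3. Coherence of A, B and any-RSV VE.** In the unadjusted setting the any-RSV odds ratio is a weighted average of the two subtype odds ratios. Take true VE of 80% (A) and 60% (B), with equal shares among unvaccinated cases: any-RSV OR = 0.5 × 0.20 + 0.5 × 0.40 = 0.30, so VE is 70%. With s_v / s_u = 0.7, A reads 1 − 0.20 × 0.7 = 86% and B reads 1 − 0.40 × 0.7 = 72%. Both exceed 70%.

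**4. A second route, through Contributor.** Section 11.12.4 allows a population-averaged model fitted with working independence, and this needs no Contributor term. Take two Contributors of equal size, coverage 10% and 40%, and true VE 0% in both.

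- Control odds: (0.10 + 0.40) / (0.90 + 0.60) = 0.333.
- Typing 90% and 40%: typed-case odds (0.09 + 0.16) / (0.81 + 0.24) = 0.238, OR 0.714, VE 28.6%.
- Typing 40% and 90%: typed-case odds (0.04 + 0.36) / (0.36 + 0.54) = 0.444, OR 1.333, VE −33.3%.

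Here typing does not depend on vaccination within a Contributor, so a Contributor fixed effect would remove the bias.

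**5. Does weighting help?** Simulation used 2,000 data sets of 1,000 cases and 4,000 controls, with true VE 70%, coverage 20% and s_u = 0.80. The weights were the inverse of the typed proportion within vaccination group.

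| s_v | Untyped cases dropped | Typed cases weighted |
|---|---|---|
| 0.56 | 78.9% | 69.9% |
| 0.64 | 76.0% | 70.0% |
| 0.80 | 69.8% | 69.8% |

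This recovery assumes that typing does not depend on subtype within vaccination group.

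**The case against.** The strongest reply is that the protocol nowhere says untyped cases are dropped from objective 2.1. The rule is stated for the primary analysis, whose outcome is RSV detection, and the wording of objective 2 describes an objective, not a missing-data instruction. This is also a master protocol, and the handling of untyped cases could be left to the SAP, which is not at hand. The promised comparison with imputed data might include subtype; with vaccination status in the imputation model, it could remove the bias.

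Much of this stands. Dropping is an inference from the only rule given, and an SAP may settle it. But the protocol does state a reason why complete-case analysis is unbiased, and that reason cannot extend to one of its own listed outcomes. The imputed-data comparison is a sensitivity analysis and is not said to cover subtype.

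A reader might also infer that subtype VE is overstated because vaccinated cases yield weaker samples. The documents do not support this. Section 13 speaks of false-negative RSV tests, and patients missed in that way never become cases. Subtyping concerns confirmed positives. It may also be missing for reasons other than sample quality, since it is collected only as far as possible. Better typing in vaccinated cases would understate VE.

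Nor does the vaccination route by itself distort the A-versus-B contrast: a typing ratio common to both subtypes cancels in the ratio of their odds ratios. Adjustment for calendar time and the Contributor fixed effect recommended for subject-specific estimates would absorb much of any variation in typing by week or site.

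**Conclusion.** The concern holds in conditional form. The complete-case justification does not reach missing subtype, and nothing else in the protocol clearly does. If untyped cases are dropped, subtype-specific VE is biased whenever typing differs by vaccination status. It may also be biased when typing and coverage both vary by Contributor and the model has no Contributor term.

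For a true VE of 60%, assumed typing ratios from 0.75 to 1.125 give 70% down to 55%; equal typing gives no bias. Direction and size in this study are unknown. Section 13 makes overstatement plausible by analogy, no more. A secondary objective is affected; the any-RSV estimate of objective 1 is not. The point is worth correcting because the remedy is cheap.

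**What to change.** In 11.12.4.1, limit the complete-case justification to exposure and covariates, and state how untyped cases are handled. For objective 2.1:

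- Restrict cases and controls alike to Contributors and periods in which subtyping was done.
- Report the typed proportion by vaccination status and by Contributor.
- Weight typed cases by the inverse of their typing probability, or multiply impute subtype among RSV-positive cases. Condition on vaccination status, Contributor, admission date, specimen type and onset-to-swab time.
- Show this result beside the complete-case estimate.
- Check that the A and B estimates are consistent with the any-RSV VE from the same restricted set.

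The data are already collected. Vaccination history and specimen types and dates are in Table 1, symptom-onset and hospitalisation dates are in the Abstract's data-collection paragraph, and Contributor is known from the data flow. The cost is a few lines in the protocol and SAP, slightly wider subtype intervals, and an assumption that subtype is missing at random given these variables.
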